17.5.2 Interim Analysis for Efficacy of Primary Endpoint: Progression Free Survival

A single interim efficacy analysis will be performed at 36 months, the calendar mid-point for the trial. Given the expected median time to progression given in Section 17.3.2, we expect to observe the progression endpoint (progression or death due to any cause) for 160 participants (83 in the folfirinox alone arm and 77 in the SBRT + folfirinox arm). After 36 months, we anticipate observing 71 progressions, which translates to 44% of the total information. Monitoring will be performed via an O'Brien-Fleming alpha spending function with an interim assessment at 44% of information time. The calculations are made assuming two-sided symmetric boundaries with a total of 2 analyses (1 interim and one final) and a total alpha 0.05. The trial will be stopped early for efficacy if the

99.695% confidence interval of the hazard ratio does not contain 1, i.e. a two-sided alpha spending of 0.00305 on the first interim analysis (0.001525 in each direction).

References

3. Burris HA, 3rd, Moore MJ, Andersen J, et al. Improvements in survival and clinical benefit with gemcitabine as first-line therapy for patients with advanced pancreas cancer: A randomized trial. *J Clin Oncol* 1997;15:2403-13.
7. Further evidence of effective adjuvant combined radiation and chemotherapy following curative resection of pancreatic cancer. gastrointestinal tumor study group. *Cancer* 1987;59:2006-10.

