7.3 Duration of Study

It is anticipated that the total duration of the study will last approximately 72 months (60 months for recruitment and a minimum of 12 months of follow-up per individual). Patients

may be followed for up to 3 years.

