16.3 Trial Monitoring

All outcome data (toxicity and efficacy) will be reviewed yearly by the Principal Investigator and key Co-Investigators. This study will also be monitored by the Stanford DSMC as stated above in Section 16.1.

Interim reports and/or study renewals will be completed every 10-12 months from study open date, which will be defined as date the study is approved by Stanford IRB. Additional and/or more frequent reports may be done if determined necessary by the study monitoring group (described in Section 11.2.3). These reports may include information about:

- Patient accrual and follow-up: overall and at each institution
- The frequency and severity of adverse events due to protocol therapy
- Compliance rates of treatment delivery with respect to the protocol prescription

Adverse event rates will be compared between treatment groups and with the stopping guideline thresholds (Section 17.5.1). With the exception of a single, planned interim efficacy analysis (Section 17.5.2), the interim reports will not contain the results from the treatment comparisons with respect the primary outcome (progression free survival) or secondary efficacy analyses. See Section 17.5 Stopping Guidelines for additional details.

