17.3.2 Sample Size Justification

Progression free survival is defined as the time from randomization until progression or death. Individuals who are lost to follow-up prior to death or progression will be censored at the date of last progression evaluation. Based upon previous research, the median progression free survival for individuals treated with mFolfinirox alone is estimated to be 6 months. A sample size of 172 randomized participants (86 per arm) has 91% power to detect an increase to 10.2 months for individuals treated with mFolfinirox plus SBRT as compared to 6 months for those receiving mFolfinirox alone assuming that the data follows an exponential distribution as well as a 60 months of accrual and a minimum of 12 months of follow-up after randomization in a 2-sided test with a type 1 error rate of 0.05.

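### The printed interim level of 0.00305 (99.695% CI) is not the value of an O'Brien-Fleming spending function at 71 of 160 events, and it is fixed at month 36 whatever the event count

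*Combined protocol and SAP*

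**What the plan says.** All of the monitoring rule is in section 17.5.2.

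- Timing: "A single interim efficacy analysis will be performed at 36 months, the calendar mid-point for the trial".
- Expected information: "After 36 months, we anticipate observing 71 progressions, which translates to 44% of the total information". The total is 160 events, 83 on chemotherapy alone and 77 with SBRT.
- Method: an O'Brien-Fleming "alpha spending function with an interim assessment at 44% of information time", with "two-sided symmetric boundaries with a total of 2 analyses (1 interim and one final) and a total alpha 0.05".
- Rule: stop for efficacy if the 99.695% confidence interval for the hazard ratio excludes 1, described as "a two-sided alpha spending of 0.00305 on the first interim analysis (0.001525 in each direction".

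The section gives no formula for the spending function. It does not say that the level will be recomputed at the observed event count, and it states no critical value for the final analysis. Section 17.3.2 gives the design test as "in a 2-sided test with a type 1 error rate of 0.05". Section 7.3 gives the timetable as "60 months for recruitment and a minimum of 12 months of follow-up per individual", about 72 months in all.

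**The concern.** The O'Brien-Fleming-type spending function has two forms in common use for a two-sided test. One spends 0.025 in each tail; the other spends 0.05 as a single function. They differ by about a factor of two at this information fraction, so a level quoted to five decimals should identify which was used. The printed level matches neither at the stated fraction.

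This number decides whether a phase III trial stops early for efficacy on its primary endpoint. Whoever runs the look needs to know whether to apply the printed level or the declared function, and the two disagree. The disagreement grows if the events at month 36 are not about 71, because the rule has a fixed confidence level while the function moves with information. Left open, the choice would have to be made when results are already visible.

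**Working it through.** **Inputs.** From 17.3.2: 86 patients per arm, exponential PFS with medians 6 and 10.2 months, 60 months' accrual plus 12 months' minimum follow-up. From 17.5.2: 71 of 160 events, total two-sided alpha 0.05. Uniform accrual is assumed.

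**Step 1: the plan's event counts reproduce.** With λ = ln 2/median and R = min(T, 60), expected events per arm at month T are (86/60)·[R − (e^(−λ(T−R)) − e^(−λT))/λ].
- T = 36: 39.4 + 32.3 = 71.7 (plan: 71).
- T = 72: 82.9 + 76.8 = 159.7 (plan: 83 + 77 = 160).

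The plan's fraction is 71/160 = 0.44375, √t = 0.6661.

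**Step 2: the interim level does not reproduce.**
- Per-tail spending, 0.025 each side: 2[1 − Φ(2.2414/√t)] per side. At 71/160 this is 2[1 − Φ(3.365)] = 0.00077 per side, 0.00153 two-sided, a 99.847% CI.
- Full-alpha spending: 2[1 − Φ(1.960/√t)] = 2[1 − Φ(2.942)] = 0.00326 two-sided, a 99.674% CI.
- Classical O'Brien-Fleming boundary c/√t, with c = 1.971 solved for total alpha 0.05: 0.00309. This is a boundary, not a spending function.

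**Step 3: rounding does not explain it.** Fractions consistent with 71, 160 and 44% after rounding run from 70.5/160.5 = 0.4393 to 0.445.

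| Method | Level over 0.4393 to 0.445 | Contains 0.00305? |
|---|---|---|
| Per-tail spending | 0.00144 to 0.00156 | No |
| Full-alpha spending | 0.00310 to 0.00330 | No |
| Classical boundary | 0.00295 to 0.00313 | Yes |

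**Step 4: where the digits do occur.** Per-tail spending at t = 0.50 gives 0.0015253 per side and 0.0030506 two-sided. These match the printed 0.001525 and 0.00305 to every digit, and 36/72 = 0.50.

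**Step 5: effect on the decision to stop, at 71 events.** The hazard ratio at the boundary is exp(−2z/√71). Under the design alternative the mean of Z is ln(10.2/6)·√71/2 = 2.236, so the chance of stopping is 1 − Φ(z − 2.236).

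| Level | z | HR to stop | Chance of stopping |
|---|---|---|---|
| 0.00305 (printed) | 2.963 | 0.495 | 23.4% |
| 0.00153 (per-tail) | 3.168 | 0.471 | 17.5% |
| 0.00326 (full-alpha) | 2.942 | 0.497 | 24.0% |

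**Step 6: effect on type I error.** From the bivariate normal with correlation √t = 0.6661:
- After 0.00305, the final bound that keeps 0.05 is z = 1.971 (p = 0.0488). A final test at 1.96 gives 0.0512.
- After 0.00153, the final bound is z = 1.964 (p = 0.0495).
- After 0.00326, it is z = 1.971 (p = 0.0487).

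**Step 7: a fixed level when events differ from 71.** As an illustration, suppose both arms had the plan's control median of 6 months. Step 1 then gives 78.8 events at month 36, or 0.492 of 160, where the function gives 0.00280 (per-tail) or 0.00522 (full-alpha). The printed rule would still use 0.00305.

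**The case against.** The strongest defence is that 0.00305 is about right on two of three readings. Full-alpha spending at 71/160 is 0.00326, and the classical boundary reaches 0.00305 at 70.8 of 160 events, which rounds to the stated 71 and 44%. To four decimals, full-alpha spending at t = 0.44 and the classical boundary at 71/160 both give 0.0031, as the printed value does. This stands as a limit on the size of the problem. It does not remove the mismatch: the plan prints five and six decimals, declares a spending function, and leaves the form unnamed.

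Several stronger readings are tempting, and the documents do not support them.

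- *The level is twice what is allowed.* This is true only for per-tail spending, which the text does not specify. Even then the chance of stopping under the alternative rises from 17.5% to 23.4%; it does not double.
- *The calendar fraction was used by mistake.* The match in Step 4 is exact, but it remains an inference.
- *Error control is lost.* A prespecified 0.00305 with the final bound solved from it keeps 0.05 overall.
- *The final test will use an unadjusted 0.05.* Section 17.3.2 states the trial's type 1 error rate, not a final nominal level. Section 17.5.2 commits to two analyses within a total of 0.05, so the final bound is derivable though unstated.
- *The 36 months run from IRB approval.* Section 16.3 defines a "study open date, which will be defined as date the study is approved by Stanford IRB", but for timing interim reports and renewals; 17.5.2 does not refer to it. The event projection works with 36 and 72 months counted from the start of randomization, so that origin is largely implied.

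**Conclusion.** The concern holds. The printed interim level is not the value of the declared function at the declared information. It is about twice too large on the per-tail form (0.00305 against 0.00153) and about 6% too small on the full-alpha form (against 0.00326). Which applies cannot be settled from the text. Separately, and on either form, one fixed confidence level at month 36 is inconsistent with spending on information time unless the events are close to plan.

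The consequence is for the evidence needed to stop early. Overall type I error lies between 0.05 and 0.0512, depending on how the final bound is set. These figures rest on 160 events as total information, 71 events at the look and, for the stopping chances, the design hazard ratio of 6/10.2. Severity is minor to should-fix: the effect is modest, but the rule should be unambiguous before the look.

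**What to change.** Amend section 17.5.2 as follows.

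1. Name the spending function and say whether alpha is spent as 0.025 per tail or as 0.05 in one function.
2. State 160 planned events as the information denominator.
3. Compute the interim level and confidence interval from the function at the events actually observed, with any printed figures labelled as planned values.
4. Replace the planned value by the one at 71/160 for the chosen form: 0.00153 with a 99.847% CI (per-tail), or 0.00326 with a 99.674% CI (full-alpha). If calendar-time per-tail spending at 36/72 was intended, declare it and keep 0.00305. If the classical boundary was intended, describe it as such and not as a spending function.
5. State that the final critical value is solved from the alpha spent and the observed information. Planned values are about z = 1.964 (p = 0.0495) after 0.00153, z = 1.971 (p = 0.0487) after 0.00326, and z = 1.971 (p = 0.0488) if 0.00305 is kept.
6. As a minor clarification, state that the 36 months run from first randomization, as the event projection implies.

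The cost is a few sentences. Sample size does not change. Power at 160 events, Φ(ln(10.2/6)·√160/2 − z), is 91.9% at z = 1.960 and 91.7% at z = 1.971, against the 91% stated in 17.3.2.

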Appendix I

EORTC QLQ-C30 and

EORTC QLQ-PAN26

EORTC QLQ-C30 (version 3)

We are interested in some things about you and your health. Please answer all of the questions yourself by circling the number that best applies to you. There are no "right" or "wrong" answers. The information that you provide will remain strictly confidential.

Please fill in your initials:

--	--	--	--	--

Your birthdate (Day, Month, Year):

--	--	--	--	--	--	--	--	--	--	--	--

Today's date (Day, Month, Year):

31

--	--	--	--	--	--	--	--	--	--	--	--

	Not at All	A Little	Quite a Bit	Very Much
1. Do you have any trouble doing strenuous activities, like carrying a heavy shopping bag or a suitcase?	1	2	3	4
2. Do you have any trouble taking a long walk?	1	2	3	4
3. Do you have any trouble taking a short walk outside of the house?	1	2	3	4
4. Do you need to stay in bed or a chair during the day?	1	2	3	4
5. Do you need help with eating, dressing, washing yourself or using the toilet?	1	2	3	4

During the past week:

	Not at All	A Little	Quite a Bit	Very Much
6. Were you limited in doing either your work or other daily activities?	1	2	3	4
7. Were you limited in pursuing your hobbies or other leisure time activities?	1	2	3	4
8. Were you short of breath?	1	2	3	4
9. Have you had pain?	1	2	3	4
10. Did you need to rest?	1	2	3	4
11. Have you had trouble sleeping?	1	2	3	4
12. Have you felt weak?	1	2	3	4
13. Have you lacked appetite?	1	2	3	4
14. Have you felt nauseated?	1	2	3	4
15. Have you vomited?	1	2	3	4
16. Have you been constipated?	1	2	3	4

Please go on to the next page

During the past week:

	Not at All	A Little	Quite a Bit	Very Much
17. Have you had diarrhea?	1	2	3	4
18. Were you tired?	1	2	3	4
19. Did pain interfere with your daily activities?	1	2	3	4
20. Have you had difficulty in concentrating on things, like reading a newspaper or watching television?	1	2	3	4
21. Did you feel tense?	1	2	3	4
22. Did you worry?	1	2	3	4
23. Did you feel irritable?	1	2	3	4
24. Did you feel depressed?	1	2	3	4
25. Have you had difficulty remembering things?	1	2	3	4
26. Has your physical condition or medical treatment interfered with your family life?	1	2	3	4
27. Has your physical condition or medical treatment interfered with your social activities?	1	2	3	4
28. Has your physical condition or medical treatment caused you financial difficulties?	1	2	3	4

For the following questions please circle the number between 1 and 7 that best applies to you29. How would you rate your overall health during the past week?

1 2 3 4 5 6 7

Very poor

Excellent

30. How would you rate your overall quality of life during the past week?

1 2 3 4 5 6 7

Very poor

Excellent

EORTC QLQ - PAN26

Patients sometimes report that they have the following symptoms or problems. Please indicate the extent to which you have experienced these symptoms or problems during the past week. Please answer by circling the number that best applies to you.

During the past week:	Not at all	A little	Quite a bit	Very much
31. Have you had abdominal discomfort?	1	2	3	4
32. Did you have a bloated feeling in your abdomen?	1	2	3	4
33. Have you had back pain?	1	2	3	4
34. Did you have pain during the night?	1	2	3	4
35. Were you uncomfortable in certain positions (e.g. lying down)?	1	2	3	4
36. Were you restricted in the types of food you can eat as a result of your disease or treatment?	1	2	3	4
37. Were you restricted in the amounts of food you could eat as a result of your disease or treatment?	1	2	3	4
38. Did food and drink taste different from usual?	1	2	3	4
39. Have you had indigestion?	1	2	3	4
40. Were you bothered by gas (flatulence)?	1	2	3	4
41. Have you worried about your weight being too low?	1	2	3	4
42. Did your arms and legs feel weak?	1	2	3	4
43. Did you have a dry mouth?	1	2	3	4
44. Have you had itching?	1	2	3	4
45. To what extent was your skin yellow?	1	2	3	4
46. Did you have frequent bowel movements?	1	2	3	4
47. Did you feel a sudden urge to have a bowel movement?	1	2	3	4
48. Have you felt physically less attractive as a result of your disease and treatment?	1	2	3	4

Please go to the next page

During the past week:	Not at all	A little	Quite a bit	Very much
49. Have you been dissatisfied with your body?	1	2	3	4
50. To what extent have you been troubled with side-effects from your treatment?	1	2	3	4
51. Have you worried about what your health might be like in the future?	1	2	3	4
52. Were you limited in planning activities in advance (e.g. meeting friends)?	1	2	3	4
53. Have you received adequate support from your health care professionals?	1	2	3	4
54. Has the information given about your physical condition and treatment been adequate?	1	2	3	4
55. Have you felt less interest in sex?	1	2	3	4
56. Have you felt less sexual enjoyment?	1	2	3	4

Appendix II

ECOG Performance Status*

Grade	Description
0	Fully active, able to carry on all pre-disease performance without restriction
1	Restricted in physically strenuous activity but ambulatory and able to carry out work of a light or sedentary nature, e.g., light house work, office work
2	Ambulatory and capable of all selfcare but unable to carry out any work activities. Up and about more than 50% of waking hours
3	Capable of only limited selfcare, confined to bed or chair more than 50% of waking hours
4	Completely disabled. Cannot carry on any selfcare. Totally confined to bed or chair
5	Dead

* As published in Am. J. Clin. Oncol.:

Appendix III

Definition of Menopausal Status:

Menopausal will be defined according to the following criteria:

Post-menopausal:

- Woman 60 years of age or older
- Woman aged 45-59 years with spontaneous cessation of menses for at least 12 months prior to registration
- Woman aged 45-59 years with cessation of menses for less than 12 months prior to registration AND an FSH level in the postmenopausal range (or >34.4 IU/L if institutional range is not available)
- Woman aged 45-59 years on hormone replacement therapy who have discontinued hormone replacement therapy at diagnosis of breast carcinoma and have an FSH level in the postmenopausal range according to institutional/laboratory standards (or 34.4 IU/L if the institutional range is not available)
- Prior bilateral oophorectomy
- Woman younger than 60 years of age who have had a prior hysterectomy (without bilateral oophorectomy) AND who have an FSH level in the postmenopausal range (or >34.4 IU/L if institutional range is not available)

Pre- or peri-menopausal: Not meeting definition for postmenopausal outlined above

Appendix IV

Eligibility Checklist

Protocol Information

Title	Pancreatic Cancer Radiotherapy Study Group (PanCRS) Trial: A Randomized Phase III Study Evaluating Modified FOLFIRINOX (mFFX) with or without Stereotactic Body Radiotherapy (SBRT) in the Treatment of Locally Advanced Pancreatic Cancer
Number	27492
Principal Investigator	[name]

Subject Information

Subject Name: _____
Study ID: _____
Gender:  Male  Female

Inclusion/Exclusion Criteria

Inclusion Criteria (From IRB approved protocol)	Yes	No	Supporting Documentation*
1. Histologically confirmed adenocarcinoma of the pancreas			
2. Induction mFOLFIRINOX up to 4 cycles			
3. Stable or better disease on re-staging scans			
4. Determined unresectable by a pancreatic cancer surgeon or a multi-disciplinary or gastrointestinal oncology Tumor Board			
5. Typically, pancreatic tumors must be < 8.0 cm in greatest axial dimension at time of treatment planning but final determination of eligibility will be based upon satisfying the radiation normal tissue constraints as specified in protocol (Section 6.1.3 - Radiation Treatment Planning).			
6. ECOG 0, 1, or 2			

7. Acceptable organ and marrow function as defined below and within 30 days of eligibility confirmation: a. Leukocytes $\geq 3,000/\mu\text{L}$ b. ANC $\geq 1,500/\mu\text{L}$ c. Platelets $\geq 50,000/\mu\text{L}$ d. Total bilirubin $\leq 1.5 \times$ institutional upper limits of normal e. AST (SGOT)/ALT (SGPT) $\leq 2.5 \times$ institutional upper limit of normal f. Creatinine not above the upper limit of normal institutional limits			
8. Ability to understand and the willingness to sign a written informed consent document			
9. Life expectancy >6 months			

Exclusion Criteria (From IRB approved protocol)	Yes	No	Supporting Documentation*
1. Children / Age <18 years			
2. Metastatic disease			
3. Prior radiotherapy to the upper abdomen/liver			
4. Prior chemotherapy for pancreatic cancer, other than up to 4 cycles of mFOLFIRINOX			
5. Uncontrolled illness including, but not limited to, ongoing or active infection (or infections requiring systemic antibiotic treatment), symptomatic congestive heart failure, unstable angina pectoris, cardiac arrhythmia, or psychiatric illness/social situations that would limit compliance with study requirements.			
6. Any concurrent malignancy other than non-melanoma skin cancer, non-invasive bladder cancer, or carcinoma in situ of the cervix. Patients with a previous malignancy without evidence of disease for > 5 years will be allowed to enter the trial.			
7. Pregnant and breastfeeding women are excluded, as well as women of child-bearing potential who are unwilling or unable to use an acceptable method of birth control (hormonal or barrier method of birth control; abstinence) to avoid pregnancy for the duration of the study. Male subjects must also agree to use effective contraception for the same period as above.			
8. Women who are not post-menopausal (as defined in Appendix III) and have a positive urine or serum pregnancy test or refuse to take a pregnancy test			

*Supporting documentation is required to confirm subject eligibility and can include but is not limited to: clinic notes, laboratory results, pathology results, radiology reports, subject self-report, or MD documentation.

IV. Statement of Eligibility

By signing this form of this trial I verify that this subject is [eligible / ineligible] for participation in the study. This study is approved by the Stanford Cancer Institute Scientific Review Committee, the Stanford IRB, and has finalized financial and contractual agreements as required by Stanford School of Medicine's Research Management Group.

Study Coordinator Signature:	Date:
Printed Name:	
Secondary Reviewer Signature:	Date:
Printed Name:	
Treating Physician Signature:	Date:
Printed Name:	

Appendix V

Case Report Form and Patient Logs:

- **Case Report Form for SAEs, AEs, and UPs**
- **Subject Log**
- **Protocol Deviation Log**
- **AE (Adverse Event) Tracking Form**

Received On: _____
Date Submitted to CCTO: _____
Date Submitted to SUMC IRB: _____

Case Report Form for SAEs, AEs, and UPs

**Protocol: *Pancreatic Cancer Radiotherapy Study Group (PanCRS) Trial:
A Randomized Phase III Study Evaluating Modified FOLFIRINOX (mFFX) with or without
Stereotactic Body Radiotherapy (SBRT) in the Treatment of Locally Advanced Pancreatic Cancer***

Stanford protocol #: 27492

OnCore #: PANC0015

Date of Report: _____

Participating Site and

Location: _____

Date of Event: _____

Subject's Initials: _____

Subject's OnCore #: _____

Research Staff Completing Form:

Name: _____

Phone: _____

Email: _____

Principal Investigator / Treating Physician at study site has reviewed and agrees with information in this report:

Printed Name: _____

Signature: _____ **Date:** _____

Answer all questions below. Provide additional pages as needed.

1. Check if event was:

- Serious Adverse Event (SAE)* Adverse Event (AE)* Unanticipated Problem (UP)#

*Note Grade: _ (According to CTCAE, V 4 or greater, available at <http://ctep.cancer.gov/reporting/ctc.html>.)

#If also UP, check that it meets criteria for: Unexpected
 Related
 Harmful

2. Check the box of which therapy the event was related or possibly related to:

- mFOLFIRINOX SBRT Other, indicate: _____

3. Indicate how much treatment the subject received up to the event:

- For mFOLFIRINOX, Cycles _____ and Days or Doses _____
- For SBRT, fractions _____ and cGy _____

4. Provide a brief description of the event, including:

- symptoms reported and when (dates)
- results of scans, labs, or other procedures or tests
- if hospital ED visit or admission, give dates and length of hospitalization
- If Grade 5, indicate date of death, primary cause, if death certificate obtained, and if autopsy performed

5. Following the event:

- Was therapy discontinued? No Yes N/A
- Was dose modified? No Yes N/A

If **Yes**, note modified dose(s): _____

-
6. Define the action plan and follow-up, including:
- Next visit and follow-up schedule if not per protocol
 - Referrals for tests, procedures, specialty or other clinics
 - Other pertinent information:
-
-
-

Protocol: *Pancreatic Cancer Radiotherapy Study Group (PanCRS) Trial: A Randomized Phase III Study Evaluating Modified FOLFIRINOX (mFFX) with or without Stereotactic Body Radiotherapy (SBRT) in the Treatment of Locally Advanced Pancreatic Cancer*

Stanford eProtocol #: 27492

OnCore #: PANC0015

Participating Center: _____

Subject Log

#	Subject Name	Subject Initials	Subject ID or OnCore #	Date On-Study (Date of Randomization)	Treatment Arm	Treatment Start Date (Day 1)	Date Off-Study	Reason Off-Study
1					 mFFX  +SBRT			
2					 mFFX  +SBRT			
3					 mFFX  +SBRT			
4					 mFFX  +SBRT			
5					 mFFX  +SBRT			
6					 mFFX  +SBRT			

7					 mFFX  +SBRT			
8					 mFFX  +SBRT			
9					 mFFX  +SBRT			
10					 mFFX  +SBRT			

Protocol: Pancreatic Cancer Radiotherapy Study Group (PanCRS)

Trial: A Randomized Phase III Study Evaluating Modified FOLFIRINOX (mFFX) with or without Stereotactic Body Radiotherapy (SBRT) in the Treatment of Locally Advanced Pancreatic Cancer

Stanford eProtocol #: 27492

OnCore #: PANC0015

Participating Center: _____

Protocol Deviation Log

#	Subject Initials	Subject ID or OnCore #	Date of Deviation	Category (see next page)	Code (see next page)	Brief Description	Date IRB notified, if applicable	Corrective Action
1								
2								
3								
4								

5								
6								
7								
8								
9								
10								
11								
12								

Deviation Categories

- A. Safety
- B. Informed Consent
- C. Eligibility
- D. Protocol Implementation
- E. Other, specify in log

Deviation Codes (associated with Deviation categories)

Safety (Category A)

1. Not reporting SAE within 24 hours
2. Laboratory tests not done
3. AE/SAE not reported to IRB
4. Other, specify on log

Informed Consent (Category B)

5. Failure to obtain informed consent
6. Consent form used was not current IRB approved version
7. Consent form does not include updates or information required by IRB
8. Consent form missing
9. Consent form not signed and dated by participant
10. Consent form does not contain all required signatures
11. Other, specify in log

Eligibility (Category C)

12. Participant did not meet eligibility criteria
13. Randomization of an ineligible patient
14. Participant randomized prior to Baseline Assessment
15. Randomization or treatment of a patient prior to IRB approval of protocol
16. Other, specify in log

Protocol Implementation (category D)

17. Failure to keep IRB approval up to date
18. Participant receives wrong treatment
19. Participant seen outside of window visit
20. Use of unallowable concomitant treatments
21. Prescribed dosing outside of protocol guidelines
22. Missed Assessment
23. Missed Visit
24. Other, specify in log

AE Tracking Form: PanCRS Trial - Phase III Rand mFFX w/ or w/o SBRT						Site:		PI:		
Pt Last Name:		Subject ID #:				Inst. MRN:		Page #:		
AE by system	Hints for grading	___ f/u visit or ___ FFX- Cycle: _____ f/u timept, if applicable: _____ Date _____  Oncore				___ f/u visit or ___ FFX- Cycle: _____ f/u timept, if applicable: _____ Date _____  Oncore				
		Lab Results/ Date:	Grade	Attribution*		Comment	Lab Results/ Date:	Grade	Attribution*	
				FFX	SBRT				FFX	SBRT
Blood/Bone marrow	Abnormals only									
WBC	low									
Hgb	low									
Hct	low									
Platelets	low									
Neut ABS/ ANC	low									
Lym ABS	low									
Other-										
Metabolic Panel	Abnormals only									
Sodium										
Potassium										
Chloride										
Creatinine	high									
Glucose										
Calcium										
Bilirubin										
AST										
ALT										
Alk phos										
Albumin	low									
Protein										
Other-										
Constitutional										
Fatigue	Affecting ADLs?									
Weight loss	< 5, 10 or 20% from baseline?									
GI										
Anorexia										
Nausea	IVF needed?									
Vomiting	Episodes/d? IVF?									
Diarrhea	BMs/d? 2/2 tx or malabsorption?									
Constipation	Last BM?									
Heartburn/dyspepsia	PPI daily?									
Upper bleed	Procedure?									
Lower bleed	Procedure?									
Ulcer	Symptoms?									
Other										
Neurology										
Periph neuropathy	Interfering w/ fxn?									
Pain										
Abdominal pain										
Other location										
Other										
Signature		Inv signature / date:				Inv signature / date:				

*Attribution - Note # under FFX or SBRT column: 1-unrelated 2-unlikely 3-possible 4-probable 5-definite
